5.2. Sample Size and Power

The study is designed to detect a difference between participants with HD and HP on HD-CAB composite score as the primary endpoint. Using a two-sided alpha level of 0.05, a sample size of at least 80 participants (40 HP and 40 participants with HD) would provide at least 80% power to detect a baseline difference in HD-CAB composite score assuming Cohen's D effect size equal to 0.63, which is in the range of effect sizes reported in the literature (Stout et al., 2014).

Using a CI approach for sample size estimation, and assuming a common SD of 1.51 in HD-CAB, a sample size of 32 evaluable participants with HD (16 per treatment arm) will provide 80% confidence level for estimating the population mean with 0.50 precision or margin of error.

Assuming a 20% dropout rate in participants with HD, a sample size of approximately 40 participants with HD will be randomized in a 1:1 ratio to SAGE-718 and placebo to obtain 32 evaluable participants with HD. Additional participants may be randomized if the dropout rate is higher than 20%.

Evaluable participants with HD are defined as those randomized participants who receive IP and have a valid baseline and at least 1 postbaseline efficacy assessment.

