5. INTRODUCTION

Huntington's Disease (HD) is a rare hereditary neurodegenerative disease characterized by specific motor symptoms, including chorea and rigidity, and deterioration of psychiatric and cognitive function. The motor symptoms can manifest at any age, after which disease progression leads to incapacitation and death. Before the appearance of motor symptoms, psychiatric and cognitive dysfunction predominate (Tabrizi 2012). Cognitive impairment is always present in the course of the disease, even in premanifest gene carriers (Cardoso 2017).

The mechanisms of cognitive changes in HD have not been fully described, but changes in glutamatergic neurotransmission appear to be involved. Reduced glutamate in the posterior cingulate cortex has been correlated with cognitive dysfunction in early manifest HD (Unschuld 2012). N-methyl-D-aspartate (NMDA) receptors are a subtype of glutamate receptor with a fundamental and well documented role in regulating synaptic strength, health, and plasticity (Vyklicky 2014, Yao 2017). NMDA receptors have been found to be dysfunctional in the postmortem brains of patients with HD (Albin 1990). Together, these data suggest that lowered NMDA receptor tone may contribute to cognitive dysfunction in HD (Paul 2013).

Preclinical data illustrate that patients with HD have reduced plasma levels of a specific oxysterol, 24(S)-hydroxycholesterol (Leoni 2013). This molecule acts as an endogenous positive allosteric modulator (PAM) of the NMDA receptor (Paul 2013) and has been correlated with performance on several cognitive tasks in HD (Lewis 2019). SAGE-718 is a novel oxysterol-based PAM of NMDA receptors with the potential to restore NMDA receptor tone to ameliorate cognitive deficits in HD. SAGE-718 only affects receptor function in the presence of endogenous glutamate, thus it does not directly activate the receptor and is not expected to cause NMDA receptor-associated excitotoxicity.

The effect of SAGE-718 on cognitive and function outcomes in participants with HD will be evaluated in a randomized, placebo-controlled, double-blind, parallel group and normative comparison study. Additional data on the effects of SAGE-718 in participants with HD will be collected throughout, including assessments of neuropsychiatric and motor symptoms.

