13.8. Sample Size and Power

Using a two-sided alpha level of 0.05, a sample size of at least 80 participants (40 HP and 40 participants with HD) would provide at least 80% power to detect baseline difference in HD-CAB composite score assuming Cohen’s D effect size equal to 0.63, which is in the range of effect sizes observed for individual tests from HD-CAB (Stout 2014).

Using a CI approach for sample size estimation a sample size of 32 evaluable participants with HD (16 per treatment arm) will provide 80% confidence level for estimating the population mean with 0.50 precision or margin of error.

Assuming a 20% dropout rate in participants with HD, a sample size of approximately 40 participants with HD will be randomized in a 1:1 ratio to SAGE-718 and placebo to obtain 32 evaluable participants with HD. Additional participants may be randomized if the dropout rate is higher than 20%.

Evaluable participants with HD are defined as those randomized participants who receive IP and have a valid baseline and at least 1 postbaseline efficacy assessment.

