Paced Tapping (Computer)	Timing, psychomotor coordination	The reciprocal of the standard deviation of the intertap intervals that occurred following cessation of the	Not defined	Not defined	Higher value indicates better performance	Not Needed; Use raw score

Subtest Name (Assessment Type)	Cognitive Function Assessed	Variables	Score Range		Interpretation of Raw value	Recode
			Min.	Max.		
		pacing tones over all trials taken (ms ⁻¹)				
Emotion Recognition (Computer)	Emotion recognition	Number of negative emotions correctly identified	0	24	High score indicates better performance	Not Needed; Use raw score

Computing HD-CAB composite scores involves following three steps. HD-CAB composite scores will be calculated per each visit per each baseline population sample mean as defined in the step 2.

Step 1: For Trail Making Test B and One Touch Stockings, reverse the score by multiplying by -1 to make higher scores indicate better performance across all the 6 subtests (See Recode column of Table 2)

Step 2: For each subtest, compute two z-scores for each participant using the formula:

$$z = \frac{\chi - \mu}{\sigma}$$

where χ is a participant's score, μ is a mean and σ is a standard deviation at baseline of

- (i) HD population sample when it is used for efficacy assessment between Sage-718 vs. placebo (if not otherwise is stated);
- (ii) Healthy population sample when it is used for the comparison of HP vs. participants with HD.

Step 3: To compute each participant's composite score, by calculating the average of six z-scores for each population sample mean.

The computation of exploratory cognitive batteries will be done as following:

- (i) Executive Function Focus Battery (EFFB) composite score will be calculated as an average of three z-scores of Symbol Digit Modalities Test (SDMT), Trail Making Test: Trail B (TMT B) and One Touch Stockings of Cambridge (OTS) for each population; If any individual subtest score is missing, the EFFT composite score will be set to missing.
- (ii) Reduced Motor Impact Battery (RMIB) composite score will be calculated as an average of three z-scores of OTS, Hopkins Verbal Learning Test-Revised (HVLT) and Emotion Recognition (ERT); If any individual subtest score is missing, the RMIB composite score will be set to missing.

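### Does the unexplained HD-CAB standard deviation of 1.51 in SAP 5.2 undermine the figure of 32 evaluable HD participants?

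*SAP*

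**What the plan says.** SAP 5.2 makes two separate sample-size statements. The first concerns the primary endpoint, the baseline difference between HD and healthy participants: 40 per group, two-sided alpha 0.05, Cohen's d of 0.63 and at least 80% power. The literature citation belongs to that effect size.

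The second concerns the randomised HD participants: "assuming a common SD of 1.51 in HD-CAB, a sample size of 32 evaluable participants with HD (16 per treatment arm) will provide" an "80% confidence level for estimating the population mean with 0.50 precision or margin of error". The number to randomise follows from it: "Assuming a 20% dropout rate in participants with HD, a sample size of approximately 40 participants with HD will be randomized in a 1:1 ratio". Protocol 13.8 has the same precision sentence ("will provide 80% confidence level for estimating the population mean with 0.50 precision or margin of error") without any SD.

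SAP 8.3.1.1 defines the composite. Each subtest is turned into a z-score and the composite is obtained "by calculating the average of six z-scores for each population sample mean". There are two reference samples. Step 2(i) uses the "HD population sample when it is used for efficacy assessment between Sage-718 vs. placebo (if not otherwise is stated"). Step 2(ii) uses the healthy sample for comparing HD with healthy participants, and SAP 8.3.3.1 adopts that scale for the primary endpoint.

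**The concern.** Three things catch the eye.

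- The value 1.51 has no stated score, reference sample, visit or source, and nothing says whether it is a level or a change from baseline. SAP 5.2 shows no redaction that would account for this.
- For SAGE-718 versus placebo, the default composite is standardised to the HD sample's own baseline. The SD of an average of six such z-scores cannot exceed about 1 at baseline, so 1.51 looks impossible.
- The 0.50 margin fits one arm's mean. The sentence opens with 32 participants, and no margin is given for the difference between the arms, although the Protocol introduction says "The effect of SAGE-718 on cognitive and function outcomes in participants with HD will be evaluated in a randomized, placebo-controlled" design.

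If the SD were wrong in a way that mattered, the basis for 32 evaluable participants would fall, and a reader could misjudge how precisely the trial can estimate a drug effect on cognition.

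**Working it through.** **Inputs.** From SAP 5.2: SD 1.51, 80% confidence (taken as two-sided), margin 0.50, 16 per arm (32 in total), 20% dropout, and d = 0.63 with 40 per group. From SAP 8.3.1.1: the composite is the mean of six z-scores. The inter-test correlations and SD ratios used below are assumptions and are not in the documents.

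**1. The plan's own figure.** The half-width for one mean is q × SD/√n.

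- n = 16, normal: 1.2816 × 1.51/4 = 0.484.
- n = 16, t with 15 df: 1.3406 × 1.51/4 = 0.506.
- n = 32: 0.342 (normal) or 0.350 (t).

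Solving for a margin of 0.50 gives n = 15 (normal) or 17 (t). The stated 16 lies between them, so 0.50 is the margin for one arm's mean. Dropout: 32/0.80 = 40, as stated.

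**2. The ceiling on the HD-standardised scale.** With mean inter-test correlation ρ, the baseline SD of the composite in its own reference sample is √((1 + 5ρ)/6).

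| ρ | SD |
|---|---|
| 0.3 | 0.65 |
| 0.5 | 0.76 |
| 0.7 | 0.87 |
| 1 | 1.00 |

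So 1.51 is out of reach for that score at baseline. Nor is it plausible as a change score on that scale. With equal SDs at both visits, the change SD is SD × √(2(1 − r)), so 1.51 needs r = 1 − 1.51²/(2 × SD²). At SD 1.0 this is 1 − 2.2801/2 = −0.14.

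**3. The other scale in the SAP.** Suppose each subtest's SD in HD participants is k times the healthy SD. The healthy-standardised composite then has SD k × √((1 + 5ρ)/6) in HD participants, with no ceiling at 1. At ρ = 0.5 and k = 2 this is 2 × 0.764 = 1.53. To reach exactly 1.51, k must be:

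- 1.51/0.645 = 2.34 at ρ = 0.3
- 1.51/0.764 = 1.98 at ρ = 0.5
- 1.51/0.866 = 1.74 at ρ = 0.7

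The documents do not give k. They do describe an impaired HD group (MoCA 15 to 25) set against a healthy group screened to normal cognition (MoCA 26 or more), and SAP 8.3.1.1 calls the HD cohort relatively progressed. A wider spread in healthy-SD units is therefore possible.

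**4. The drug-placebo difference.** The standard error is SD × √(2/16).

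- SD 1.51: standard error 0.534; 80% half-width 0.684 (normal) or 0.700 (t, 30 df). A margin of 0.50 would carry about 64% confidence, and holding it at 80% would take 31 per arm (t).
- SD 1.0, the HD-standardised ceiling: standard error 0.354; 80% half-width 0.453 (normal) or 0.463 (t).
- ρ from 0.3 to 0.7 on the HD-standardised scale (SD 0.65 to 0.87): about 0.29 to 0.40 at 80%.

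If the analysed score is the HD-standardised composite, with an SD no larger than its baseline ceiling, even the difference has an 80% margin inside 0.50.

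**5. The primary power statement.** With d = 0.63 and 40 per group, power is 0.804 (normal) or 0.795 (t), which agrees with the stated 80% to rounding. The calculation does not use 1.51.

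**The case for a change.** The strongest case for a change is that 32 evaluable participants is a stated target, that this one sentence is its only stated justification, and that its key input cannot be traced. The only scale the SAP assigns by default to SAGE-718 versus placebo excludes a baseline SD of 1.51. A reader who takes 0.50 as the precision of the randomised comparison would be too optimistic at the sponsor's own SD, because 0.70 is 40% wider than 0.50 (0.70/0.50 = 1.40). The remedy would cost two or three sentences.

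Part of this stands. The scale and source of 1.51 are missing, and adding the words per arm to the margin would help. The rest is weaker. The sentence gives the 16 per arm beside the margin and speaks of a population mean, so it does not present 0.50 as the margin for a difference. It is also not tied to the HD-standardised score, so the ceiling of 1 bites only under a reading that the text does not state. The visible primary objective is the HD versus healthy baseline difference, and the visible secondary objective is safety and tolerability. Other objectives and analyses are redacted, and no readable text promises precision for a drug-placebo contrast. Replacing 1.51 with 1.0 would be no improvement, since 1.0 is a limit reached only if all six tests correlate perfectly.

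**Conclusion.** No change to the plan is needed. The precision statement is arithmetically right for one arm of 16 (0.484 to 0.506 against a stated 0.50). The value 1.51 is unexplained, but the documents do not show it to be wrong. It is impossible for the HD-standardised baseline composite (maximum about 1). It is possible on the healthy-standardised scale if HD subtest SDs are roughly 1.7 to 2.3 times the healthy ones, assuming inter-test correlations of 0.7 down to 0.3. If it is too high for the score eventually analysed, the true intervals will be narrower than the plan implies.

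The drug-placebo half-width at 80% would be 0.68 to 0.70 at SD 1.51 and 0.46 at SD 1.0. Anyone who wants that figure can derive it from the stated SD and arm size, and the final analysis can form its intervals from the observed SD rather than from 1.51. No visible decision rule uses 1.51 or 0.50. Enrolment, the analyses and the primary power statement would be the same with or without the missing detail. This is a reporting gap, and filling it would change no result or conclusion.

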5.3. Randomization

This is a randomized, placebo-controlled, double-blind, parallel group study. Eligible participants with HD will be randomized 1:1 in a stratified manner by previous intake of antisense oligonucleotide (ASO) drugs (yes/no) to receive SAGE-718, or matching placebo for 28 days. Stratified randomization will ensure the treatment balance within each stratum of prior antisense oligonucleotide drug intake (yes or no) with the consideration that participants with or without prior exposure to antisense oligonucleotide drug may respond to treatment differently. Randomization will take place on Day 1.

Randomization will be performed centrally via an interactive response technology (IRT) system. Randomization schedules will be generated by an independent statistician. The allocation to treatment group will be based on the randomization schedule.

Similarly for HP on Day 1, site staff will access the IRT and provide the necessary participant identifying information, including participant identification (ID) number assigned at Screening to register the eligible HP in the IRT system as enrolled status, and set as inactive for treatment assignment.

5.4. Blinding and Unblinding

Participants, clinicians, and the study team will be blinded to treatment allocation during the study. The randomization schedules will be kept strictly confidential, accessible only to authorized personnel until the time of unblinding. The blinding of the study will be broken after the database has been locked.

During the study, the blind can be broken by the investigator via the IRT system only when the safety of a participant with HD is at risk and the treatment plan is dependent on the study treatment received. Unless a participant with HD is at immediate risk, the investigator should make attempts to contact Sage prior to unblinding the study treatment administered to a participant with HD. The responsibility to break the treatment code in emergency situations resides solely with the investigator. If the unblinding occurs without Sage's knowledge, the investigator must notify Sage within 24 hours of breaking the blind. All circumstances surrounding a premature unblinding must be clearly documented in the source records.

In all cases where the study personnel are unblinded, pertinent information (including the reason for unblinding) must be documented in the participant's source documentation and on the eCRF. At the time of withdrawal from the study/stopping participation, if possible, an ET visit should be conducted.

6. MODIFICATIONS

6.1. Modifications from the Approved Clinical Study Protocol

- Adding stratification factor of previous intake of antisense oligonucleotide drugs (yes/no) to all analyses done with [REDACTED].
- Change from baseline in concomitant medications will not be analyzed. Concomitant medications will be summarized.
- Full Analysis Set definition was updated to clarify HP and HD participants inclusion.
- All Randomized Set was replaced by All Enrolled to better describe the study participants.
- Two exploratory cognitive batteries were created to separately examine SAGE-718 effects on (1) tests of the executive function domain, referred to as the Executive Function Focus battery (EFFB) and (2) tests utilizing response formats that minimize demands on psychomotor speed and coordination, referred to as the Reduced Motor Impact battery (RMIB). The latter battery is intended to inform the utility of the HD-CAB in participants where motor symptoms may impede or otherwise confound performance of certain tests. The EFFT consists of Symbol Digit Modalities Test (SDMT), Trail Making Test: Trail B (TMT B) and One Touch Stockings of Cambridge (OTS). The RMIB consists of OTS, Hopkins Verbal Learning Test-Revised (HVLT) and Emotion Recognition (ERT).

A series of horizontal black bars of varying lengths, likely a redacted list or a decorative element.

6.2. Modifications from the Approved Statistical Analysis Plan

This is the first version of the statistical analysis plan for final analysis.

6.3. Modifications from the Approved DMC Charter

Not applicable.

7. ANALYSIS SETS

7.1. Efficacy Analysis Sets

Full Analysis Set: The Full Analysis set (FAS) will include all randomized HD participants and all HP who meet the eligibility criteria and have at least one baseline assessment of HD-CAB (participants with HD and HP) and will be used in the analysis of primary endpoint.

Full Analysis Set 1: The Full Analysis Set 1 (FAS1) will include all participants who initiate IP and have baseline and at least one postbaseline efficacy evaluation (participants with HD only). For participants with HD the efficacy endpoints will be analyzed according to the treatment the participant is randomized to.

Full Analysis Set 2: The Full Analysis Set 2 (FAS2) will include all participants with HD who initiate IP or HP who meet eligibility criteria and have baseline and at least one postbaseline efficacy evaluation (participants with HD and HP). For participants with HD the efficacy endpoints will be analyzed according to the treatment the participant is randomized to.

Healthy Participants Set: The Healthy Participant Set (HPS) will include all HP who meet eligibility criteria and have at least one baseline assessment and one postbaseline assessment of at least one of the following tests: HD-CAB [REDACTED]
[REDACTED]

7.2. Safety Analysis Sets

Safety Set: The Safety Set (SS) will include all participants with HD who were administered IP or HP who met eligibility criteria and will be used to describe the safety data. The Safety Set will be further subdivided to describe participants with HD and HP separately.

Safety Set 1: The Safety Set 1 (SS1) will include all participants with HD in the safety analysis set.

Safety Set 2: The Safety Set 2 (SS2) will include all healthy participants in the safety analysis set.

7.3. Other Analysis Sets

All Enrolled Set: All Enrolled Set will include all randomized HD participants and all HP who meet the eligibility criteria and will be used to describe participant disposition and protocol deviations.

[REDACTED]
[REDACTED]

8. STATISTICAL ANALYSIS

8.1. General Considerations

Continuous data will be summarized in terms of the number of participants, mean, standard deviation (SD), minimum, and maximum. The minimum and maximum will be reported to the same number of decimal places as the raw data recorded in the database. The mean and median will be reported to one more decimal place, and the SD (and the standard error [SE], if applicable) will be reported to two more decimal places, than the raw data recorded in the database. In general, the maximum number of decimal places reported shall be four for any summary statistic. Any values that require transformation to standard units (metric or SI) will be converted with the appropriate corresponding precision.

Categorical data will be summarized in terms of the number of participants providing data at the relevant time point (n), frequency counts, and percentages. Percentages will be reported to one decimal place unless otherwise specified. Any planned collapsing of categories will be detailed in the SAP text and the data displays.

Percentages will not be presented for zero counts. Percentages will be calculated using the number of participants (n) as the denominator. A missing category shall be included only for categorical variables where no data is available. The missing category will be omitted if there are no missing values for that variable.

For the laboratory results that are “ $\leq x$ ” or “ $\geq x$ ”, where x is a number as collected in the data, the numeric part of the result will be used in the calculation in the summary tables. If a laboratory value contains ‘y <’ then y minus 0.1 for values measured to the first decimal place, 0.01 for values measured to the second place, 0.001 for values measured to the third decimal place, and so on, will be used for the analysis. If a laboratory value contains ‘z >’ then z plus 0.1 for values measured to the first decimal place, 0.01 for values measured to the second place, 0.001 for values measured to the third decimal place, and so on, will be used for the analysis. The same is true if the result is presented as below limit of quantification (BLQ) and a lower limit of quantification (LLOQ) value is provided – LLOQ value will be used for calculation in the summary tables. The actual results as collected will be displayed in the listings.

P-values greater than or equal to 0.0001, in general, will be presented to four decimal places. P-values less than 0.0001 will be presented as “<0.0001”. P values greater than 0.9999 will be presented as “>0.9999”.

Confidence intervals will be presented to one more decimal place than the raw data.

All summaries and figures will be provided by treatment group – either by randomized treatment or actual treatment received depending on the analysis set being used. Actual treatment is defined as: SAGE-718 or Placebo.

Participants who are randomized to 1.2 mg treatment will be summarized under SAGE-718 group. For efficacy data analysis, participants’ data are analyzed by randomization assignment. For safety data analysis, participants’ data are analyzed per the actual treatment

received, and this is determined as follows: if a participant received any dose of SAGE-718 at any point of time, the participant is assigned to actual treatment of SAGE-718.

All participant data, including those derived, to support tables and figures will be presented in the participant data listings. In general, the participant data listings will be sorted by participant number and assessment visit and date (and time, if applicable). The treatment will be identified for each participant.

General definitions are defined as below:

- Baseline for participants with HD is defined as the last non-missing measurement prior to the first dose of IP, unless stated otherwise. If the time of an assessment is collected, baseline will be the latest assessment prior to first dose of IP administration time; if the time of an assessment is not collected, the assessment on Day 1 is assumed to be prior to dosing if the protocol mentions that this assessment needs to be before dosing, or it is collected as “pre-dose”.
- Baseline for HP is defined as the last non-missing measurement on or prior to Day 1.
- Study day 1 is defined as the date of randomization for untreated randomized HD participants or the date of first dose for treated HD participants.
- Study day 1 is defined as the date of completion of the baseline assessments for HP.
- Study day will be calculated relative to Study day 1.

If event is prior to Study day 1, then study day is calculated as:

$$\text{Date of Event} - \text{Date of Study day 1}$$

If event is after Study day 1, then study day is calculated as:

$$\text{Date of Event} - \text{Date of Study day 1} + 1$$

